6.5 POOLING OF CENTRES

Given the low number of patients per centre and the primarily descriptive nature of the statistical analysis, separate analyses by centre are not meaningful and not desirable.

6.6 HANDLING OF MISSING DATA AND OUTLIERS

6.6.1 Withdrawals

The reasons for withdrawal from treatment will be reported as indicated on the eCRF.

6.6.2 Efficacy data

Binary efficacy endpoints

The primary imputation approach for binary endpoints will be No Response Imputation (NRI) described below.

1. If a patient prematurely discontinues study medication administration for any reason, then all data subsequent to the discontinuation will be considered to be missing. The cut-off date to be used is the last dose of study medication administration + 4 weeks (including the extended time windows).
2. For endpoints which are measured at multiple visits, if there are data at visits both before and after the visit with a missing outcome, then impute as success (a responder) only if both neighbouring visits also represent a success (independent of whether the preceding and following observations were selected for analysis based on time windows described in [Section 6.7](#)).

For all patients with a missing visit outcome, impute as a failure to achieve a response (non-responder).

In addition, for all binary endpoints (i.e. endpoints that are either 1 (patient responded) or 0 (patient did not respond)), frequency tables with observed data will be presented.

Categorical efficacy endpoints with more than two outcomes

Some endpoints or their subscores are categorical with more than two potential outcomes (e.g. IGA, DLQI). As a general rule, imputation will only be applied on the complete score. In case if a categorical subscore is analysed separately, no imputation will be applied (only observed data will be analysed).

Continuous efficacy endpoints

For efficacy endpoints which are continuous in nature, the use of a restricted maximum likelihood (REML)-based mixed model repeated measures (MMRM) approach, if applicable, will ensure that missing data are handled implicitly, via a missing at random assumption, by the statistical model.

[figure not shown]

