3.3.4.1 Discontinuation of trial treatment

An individual patient will discontinue trial treatment if:

- The patient wants to discontinue trial treatment, without the need to justify the decision.
- The patient has repeatedly shown to be non-compliant with important trial procedures and, in the opinion of both, the investigator and sponsor representative, is not willing or able to adhere to the trial requirements in the future.
- The patient needs to take concomitant medication that interferes with the investigational medicinal product or other trial treatment, please see Section [4.2.3](#).
- The patient can no longer receive trial treatment for medical reasons (such as surgery, adverse events, other diseases, or pregnancy).

- For individual stopping rules related to specific adverse events, please see Section [4.2](#).

In case of a temporary discontinuation of trial treatment, trial treatment should be restarted as soon as medically justified, please see Section [4.1.4](#), [4.2.2](#). Even if the trial treatment is discontinued, the patient remains in the trial and, given his/her agreement, will undergo the procedures for early treatment discontinuation and follow up as outlined in the [Flow Chart](#) and Section [6.2.3](#).

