4.2 OTHER TREATMENTS, EMERGENCY PROCEDURES, RESTRICTIONS

4.2.1 Other treatments and emergency procedures

Stable doses of concomitant therapies for chronic conditions, for which neither the condition nor the treatment are judged to exclude the patient from participation (see Section [3.3](#)), are permissible. All concomitant medications should be carefully evaluated by the investigator and the Clinical Trial Manager should be contacted when there are questions regarding concomitant medications.

Proprietary confidential information © 2020 Boehringer Ingelheim International GmbH or one or more of its affiliated companies

During the trial, if the severity and progression of the disease worsens, the investigator can treat the patient with Standard of Care (SoC) of his/her choice. All efforts should be made to inform the patient of the importance of coming to the protocol specified visits (See [Flow Chart](#)) up to the EoS visit. Patients refusing to return to the study site for scheduled visits after the end of treatment should at least provide safety information by phone at the respective visits.

Overall, the choice of the escape treatment i.e Standard of Care treatment will be left at the discretion of the investigator. The sponsor will not provide/supply SoC treatment(s) to the sites. If a patient receives escape treatment the decision to maintain the patient on trial treatment will be decided with discussion between the investigator and sponsor.

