¹In case of disease worsening, the use of standard of care (physician's choice) is left at the discretion of the investigator (refer to Section [4.2.1](#)). Patient continuation on trial treatment will be reassessed based on the medication used for the disease worsening.

²This list is not all inclusive, for any medications that are not listed, contact the Clinical Trial Manager (CTM) for restriction duration

³ Other antihistamines for indications other than atopic dermatitis can be prescribed on an as-needed basis. Dose should, preferably, be stable within one week prior to V2 and during the course of the study.

⁴ No restriction on corticosteroid drops administered in the eye or ear; nasal corticosteroids to treat rhinitis;inhaled corticosteroids to treat asthma; Montelukast (systemic) to treat asthma or allergic rhinitis - if these medications were on stable maintenance dose for 3 months prior to Visit 2.

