6.2.3 Trial Completion and End of Residual Period

For all randomized patients termination of trial medication and trial completion must be recorded on the corresponding eCRF.

For the comprehensive list of the trial procedures required following the end of treatment, please refer to [Flow Chart](#).

Trial Completion:

Trial completion is defined as a patient having reached the EoS visit within the specified window per protocol.

Treatment Completion:

Treatment completion is defined as a patient receiving four (4) infusions of trial drug (BI 655130 or placebo) at V2, V4, V5 and V6.

Proprietary confidential information © 2020 Boehringer Ingelheim International GmbH or one or more of its affiliated companies

In the re-allocation period (V7 to V11) treatment completion is defined as:

- non-responder patient receiving 4 infusions of BI 655130 at V7, V8, V9, V10 and continuing in the trial until the last visit (V11) – End of Study/FU1 (Week 32 - 44).
- responder continuing in the trial until the last visit (V10) – Week 28 or until they reach a 50% reduction in EASI score compared to baseline

Early Treatment Discontinuation:

In case the infusion of study drug is permanently discontinued before the whole amount of prepared solution has been administered to the patient, every effort should be made to keep the patient in the trial and complete all of the remaining study visits. If this is not possible, assessments of the primary endpoint V7 (Week16), should be completed or at a minimum an early EoS visit. Please refer to the [Flow Chart](#).

Early Trial Discontinuation:

A patient not having reached the EoS visit within the specified window per protocol (e.g. due to withdrawal of consent, lost to follow-up, death etc.).

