5.2.2 Secondary endpoints

The secondary endpoints are listed below.

- Drug-related Adverse Events (AEs)

Numbers and percentages of patients with drug-related AEs will be presented.

- Change from baseline in EASI Score at Week 4

The absolute and percent change from baseline as well as the absolute values at visits will be analysed.

- EASI50/75 responders at Week 4 and 16

Numbers and percentages will be analysed.

Achievement of Decrease in EASI \geq xx% (EASIxx)

Achieving a response of xx% or larger decrease from baseline in EASI score is denoted as EASIxx. The EASIxx represents a binary variable with values of 0 (= non-response) or 1 (=response).

It is calculated based on the following approach (with xx taking a value of 50 or 75):

$$\text{If } \left\{ \frac{\text{EASI(BL)} - \text{EASI(current)}}{\text{EASI(BL)}} \times 100 \right\} \geq xx \text{ then EASIxx}=1,$$

else EASIxx = 0.

- Change from baseline in SCORing of Atopic Dermatitis (SCORAD) at Week 4 and 16

The absolute and percent change from baseline as well as the absolute values at visits will be analysed.

The SCORAD consists of three elements: extent of disease, intensity of disease, and subjective symptoms (Pruritus and Sleep Loss). It sums up to a maximum of 103 points. Two of the SCORAD items are subjective symptoms (C) assessed on Visual Analog Scales (VAS) from 0 to 10: Pruritus VAS and Sleep Loss VAS.

The following formula will be used to calculate the SCORAD element assessing the Extent of the disease:

$$\text{Extent Score}(A) = (\text{Face}_{\text{Front}} \times 4.5 + \text{Upper_Limbs}_{\text{Front}} \times 9 + \text{Trunk}_{\text{Front}} \times 18 + \text{Lower_limbs}_{\text{Front}} \times 18 + \text{Genitals}_{\text{Front}} \times 1 + \text{Head}_{\text{Back}} \times 4.5 + \text{Upper_limbs}_{\text{Back}} \times 9 + \text{Trunk}_{\text{Back}} \times 18 + \text{Lower_limbs}_{\text{Back}} \times 18) / 100$$

In the SCORAD element assessing the Intensity of the disease the following scoring will be used:

- 0 for "Absence"
- 1 for "Mild"
- 2 for "Moderate"
- 3 for "Severe"

The SCORAD Intensity score element will be derived using the formula below:

$$\text{Intensity Score}(B) = (\text{Erythema_Score} + \text{Edema/Papulation_Score} + \text{Oozing/crusts_Score} + \text{Excoriations_Score} + \text{Lichenification_Score} + \text{Dryness_Score})$$

For the SCORAD element subjective symptoms the following formula will be used:

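### EASI50/75 and IGA 0/1 at a visit attended after escape steroids are scored as observed, because the visible imputation rules act only on stopping trial drug or missing a visit

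*SAP*

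**What the plan says.** SAP 6.6.2 gives the imputation rules for binary endpoints. Rule 1 reads: "If a patient prematurely discontinues study medication administration for any reason, then all data subsequent to the discontinuation will be considered to be missing". Its cut-off is the last dose plus four weeks, extended windows included. Rule 2 allows a missing visit to count as a success when both neighbouring visits are successes. Every other missing visit outcome is imputed as non-response. Protocol 7.5 has the missing-visit rule only.

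The response definitions carry no medication condition. SAP 5.2.2 states: "Achieving a response of xx% or larger decrease from baseline in EASI score is denoted as EASIxx". IGA response is defined from the score in the same way.

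Protocol 4.2.1 permits standard of care of the investigator's choice on worsening and adds: "If a patient receives escape treatment the decision to maintain the patient on trial treatment will be decided with discussion between the investigator and sponsor". Footnote 1 to Protocol Table 4.2.3.1: 1 says: "Patient continuation on trial treatment will be reassessed based on the medication used for the disease worsening". Protocol 3.3.4.1 lists as a reason to stop: "The patient needs to take concomitant medication that interferes with the investigational medicinal product or other trial treatment", and refers to Section 4.2.3 for detail.

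SAP Table 6.2: 1, codes D2.01a to c, lists restricted medication, systemic steroids and skin-related steroids as important deviations that may affect efficacy data. It excludes these patients from no analysis set. SAP 7.2 tabulates atopic dermatitis medication used in the double-blind period. SAP 7.5.2.1 analyses EASI50/75 by logistic regression with a risk difference (CMH as sensitivity) and IGA response by CMH.

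**The concern.** The protocol restricts these drugs because they treat the disease being measured, and then allows them as escape. A patient who worsens, receives steroids, improves and attends the visit can meet EASI50, EASI75 or IGA 0/1 because of the steroids. Nothing visible in the scoring rules prevents that visit from counting as a response to the randomised treatment. The arms are small, so a few such patients can visibly move the response rates and the risk difference that the SAP will report. The deviation list shows that the SAP foresees the influence, but it attaches no scoring consequence to it.

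**Working it through.** **Which visits the discontinuation rule reaches.** Inputs: blinded infusions at V2, V4, V5 and V6 (Protocol 6.2.3); planned Days 1, 29, 57 and 85, with Week 4 on Day 29 (extended window Days 22 to 42) and Week 16 on Day 113 (extended window from Day 99), from SAP Table 6.7: 1; cut-off = last dose + 28 days (SAP 6.6.2).

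| Last blinded infusion received | Cut-off | Attended Week 4 visit | Attended Week 16 visit |
|---|---|---|---|
| 1st (Day 1) | 1 + 28 = Day 29 | scored as observed | set to missing, then non-response |
| 2nd (Day 29) | 29 + 28 = Day 57 | scored as observed | set to missing, then non-response |
| 3rd (Day 57) | 57 + 28 = Day 85 | scored as observed | set to missing, then non-response |
| 4th (Day 85) | 85 + 28 = Day 113 | scored as observed | scored as observed |

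At Week 4 the rule never applies to an attended visit on the planned schedule, whether or not drug is stopped. At Week 16 it does not apply to anyone who had all four infusions, including a patient who starts steroids between Weeks 12 and 16. Protocol 6.2.3 counts that patient as complete: "Treatment completion is defined as a patient receiving four (4) infusions of trial drug". Stopping and continuing are scored differently only at Week 16, for patients who stop after the first, second or third infusion.

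**Other visible text that might catch the case.** The missing-visit rule does not apply to an attended visit. The additional observed-data frequency tables in SAP 6.6.2 count the post-escape visit too. The completer set (SAP 6.3) keeps an escaped patient who stayed on drug. The visit-selection rules (SAP 6.7) and the binary analyses (SAP 7.5.2.1) do not mention medication.

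**Size.** The plan gives no escape rate and no assumed response rate, so it has no figure of its own to reproduce here. Only whole-patient counts are used, with 30 active and 15 placebo patients (Protocol synopsis).

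- One patient in the active arm: 1/30 = 3.3 points.
- One patient in the placebo arm: 1/15 = 6.7 points.
- Change in unadjusted risk difference, active minus placebo, for a active and p placebo responders who count only because post-escape visits are scored as observed: a/30 − p/15.

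| a | p | Change in risk difference (points) |
|---|---|---|
| 0 | 1 | 0 − 6.7 = −6.7 |
| 1 | 1 | 3.3 − 6.7 = −3.3 |
| 1 | 2 | 3.3 − 13.3 = −10.0 |
| 2 | 1 | 6.7 − 6.7 = 0.0 |
| 1 | 0 | +3.3 |
| 3 | 1 | 10.0 − 6.7 = +3.3 |

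The counts are illustrative. With 2:1 allocation, one such patient in each arm does not cancel out.

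**The case against.** **The rule may exist in text we cannot see.** SAP 5 refers to Section 6.6 for sensitivity analyses, but none is labelled as such in the visible part. The completer set is defined but used in no visible analysis. Parts of 6.6 and all of 7.4.2 are withheld, and text is missing within 7.5.2.1. This stands: the finding is that no rule is visible, and the fix is conditional on that.

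**Scoring attended visits as observed is a legitimate treatment-policy choice.** It fits the intent-to-treat full analysis set. In part this stands, and it is why the primary analysis can stay as it is. It is weaker for the binary endpoints, where the SAP already discards data after premature discontinuation. If as-observed scoring after escape is intended, the SAP should say so and show the alternative.

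**A reader might infer that the plan always scores stopping drug as failure and continuing as success, so that like patients are treated differently throughout.** The dates do not support this. The difference exists only at Week 16 after infusions one to three. Nor does it turn on the continuation decision alone, since footnote 1 ties that decision to the medication used.

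**A reader might infer that the protocol leaves interfering medication undefined.** It does not: Protocol 3.3.4.1 refers to Section 4.2.3, whose table lists topical corticosteroids and systemic steroids. Footnote 1 nevertheless leaves continuation after escape to judgement.

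**Scoring escape as failure could penalise escape more than stopping.** That would hold only if the rule were limited to patients still on drug. Applied whether or not drug continues, it treats both alike.

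**No effect is demonstrated.** True. Data-review meetings may also decide whether discrepant values are used (SAP 6.2), and Protocol 7.3 says sensitivity analyses may be needed. Neither is a prespecified scoring rule.

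**Conclusion.** The concern holds for the visible text. An attended Week 4 or Week 16 visit after escape steroids is scored as observed for EASI50/75 and IGA 0/1, and a steroid-assisted response is credited to the randomised arm. Each such patient moves the active rate by 3.3 points or the placebo rate by 6.7 points, assuming all 30 and 15 patients are analysed and rates are unadjusted.

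The documents do not support a claim that the drug effect is understated or overstated, because escape frequency by arm is not given. They also do not support a claim that the whole SAP lacks an escape rule, given the withheld sections. It would be wrong to infer that the primary analysis is free of the issue: no visible rule removes post-escape EASI values from the MMRM either. That as-observed handling can stay. SAP 7 calls all efficacy analyses exploratory and these endpoints are secondary, so this is a correction that should be made, not one on which the trial's main result depends. Confidence is medium because of the withheld text.

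**What to change.** Unless a withheld section already does so, add to SAP 6.6.2:

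- Week 4 and Week 16 binary outcomes count as non-response at visits after the start, in the blinded phase, of atopic dermatitis escape or restricted medication in the D2.01a to c classes, whether or not trial drug continues. Rule 2 is not applied to these visits.
- The qualifying medications are listed by class, blinded and before the Week 16 lock, so that scoring does not rest on patient-by-patient judgement. Use permitted by footnote 4 of Protocol Table 4.2.3.1: 1 (for example "No restriction on corticosteroid drops administered in the eye or ear") does not qualify.
- Where a partial start date leaves the order of medication and visit unknown, the result is reported both ways. The first-of-month rule in SAP 6.6.3 alone could date a drug before a visit it actually followed and turn a genuine response into a failure.
- The logistic and CMH analyses are repeated with post-escape values as observed and missing visits still imputed as now. Both sets are presented.
- This scoring does not alter the Week 16 re-allocation.

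The cost is SAP wording, an extension of the planned blinded deviation review to escape use not coded as a deviation, and one re-run of the binary analyses. The medication data are already planned for tabulation (SAP 7.2).

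There are downsides. A short escape course counts as failure through Week 16. Percent change in EASI and EASI75 would handle escape differently, and some patients re-allocated as Responders would appear as EASI75 non-responses. The efficacy table needs a footnote explaining both.

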6.6.3 Safety data

[figure not shown]
From CTP Section 7.5: *With respect to safety evaluations, it is not planned to impute missing values.*

The only exceptions where imputation might be necessary for safety evaluation are AE dates and start and stop dates for concomitant medications. Missing or incomplete AE dates are imputed according to BI standards (see BI-KMED-BDS-HTG-0035 (4)).

Partial start and stop dates for concomitant medications will be imputed to enable subsequent calculation (but not for display) by the following "worst case" approach:

- If the day of the end date is missing, then the end date is set to last day of the month (or to the patient's trial completion date, if it is earlier than the last day of the month).
- If the day and month of the end date are missing then the end date is set to 31st of December of the year (or to the patient's trial completion date, if it is earlier than the 31st of December of the year).
- If the day of the start date is missing the start date is set to first day of the month.
- If the day and month of the start date are missing then the start date is set to 1st January of the year.
- All other cases need to be assessed by the trial team on an individual basis, using the above points as guidance.

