C1.02	
Wrong kit assigned to the patient.
 
LABEL: Wrong medication assigned.
	
After unblinding check the numbers of kits assigned by IRT system versus the randomised treatment.
	None
C1.03	
Patient treated without randomisation.
 
LABEL: Treatment without randomisation.
	
Patient treated according to eCRF, but not randomised according to IRT.
	None
C2	Non-compliance		
C2.01	
Non-compliance with study drug administration - administered dose too high
 
LABEL: Too high dose taken
	
The dose administered above 600 mg
	
None

C2.02	
Non-compliance with study drug administration - administered dose too low
 
LABEL: Too low dose taken
	
The dose administered below 600 mg
 
Check versus total infusion volume reported on the eCRF
	
None

Table 6.2: 1 (cont'd) Important protocol deviations

Category / Code	Description	Comments	Excluded from ¹
C3	Incorrect trial medication dispensed		
C3.01	Incorrect trial medication dispensed	This could be e.g. the case if wrong medication was dispensed by investigator at any visit after randomisation visit. After unblinding it needs to be checked whether this is an iP.D.	None
LABEL: Incorrect trial medication dispensed			
D	Concomitant medication		
D1	Previous medication		
D1.01	Washout of previous medication too short	Check versus concomitant medication end date	None #
LABEL: Washout too short.			
D2	Prohibited medication use		
D2.01a	Use of restricted medication (other than steroid) with potential influence on efficacy data	Manual review versus listing of concomitant medication	None #
LABEL: Restricted medication other than steroid.			
D2.01b	Use of restricted medication (systemic steroid) with potential influence on efficacy data	Manual review versus listing of concomitant medication	None #
LABEL: Restricted medication (systemic steroid).			
D2.01c	Use of restricted medication (skin-related steroid) with potential influence on efficacy data	Manual review versus listing of concomitant medication	None #
LABEL: Restricted medication (skin-related steroid).			

Table 6.2: 1 (cont'd) Important protocol deviations

Category / Code	Description	Comments	Excluded from ¹
F	Study specific analysis		
F1	Other trial specific violation		
F1.01	Study drug intake too early (i.e., <14 days after the previous intake) LABEL: Study drug intake outside time window (<14 days)	Check actual visit dates	None

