7.2 CONCOMITANT DISEASES AND MEDICATION

Analyses of concomitant diseases and medication will be based on the RS.

Concomitant diseases will be coded according to the most recent version of MedDRA.

Concomitant medication will be coded according to the most recent version of the World Health Organisation – Drug Dictionary.

Concomitant diseases which are present at start of the study, as well as characteristics of the trial disease, will be descriptively summarized by treatment.

A medication will be considered concomitant to treatment, if it

- is ongoing at the start of trial treatment or
- starts within the on-treatment period (see [Section 6.1](#) for a definition of study analysis phases).

Concomitant medication use will be summarised with frequency and percentage of patients by ATC3 class and preferred name. Summaries will be presented for:

- historical medication taken before the first study drug administration of the double-blind period (i.e., the start and stop dates are before the date of the first study medication infusion)
- concomitant medication that started before the double-blind treatment (i.e., concomitant medication start date was prior to first study treatment administration)
- concomitant medication started and taken within the double-blind period (from the day of the first treatment administration to the date of the Week 16 visit – 1 day)
- concomitant medication that started on or after the Week 16 (V7) visit date (i.e., concomitant medication start date was on the Week 16 visit date or thereafter)

The frequency and percentage of patients with previous medication for AD will be displayed as per data collected in the eCRF (i.e., separately for topical, non-topical, and non-topical/non-drug therapies). Frequencies by preferred name and treatment arm will be displayed.

Concomitant use of non-drug therapies will be summarized with frequency and percentage. Summaries will be presented for

- historical non-drug therapies taken before the first study drug administration of the double-blind period (i.e., the start and stop dates are before the date of the first study medication infusion)
- concomitant non-drug therapies that started before the double-blind treatment (i.e., concomitant non-drug therapy start date was prior to first study treatment administration)
- concomitant non-drug therapies started and taken within the double-blind period (from the day of the first treatment administration to the date of the Week 16 visit – 1 day)

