- concomitant non-drug therapies that started on or after the Week 16 (V7) visit date (i.e., concomitant non-drug therapy start date was on the Week 16 visit date or thereafter)

In addition, the frequency and percentages of patients with concomitant AD medication used during the double-blind period (i.e., starting at baseline visit or thereafter) will be displayed by ATC3 and preferred name and by treatment.

The relevance of the concomitant therapies to the evaluation of PK will be decided no later than at the RPM/DBLM.

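### SAP 6.6.3 sets no floor at first dose for partial medication start dates, so some medication started on blinded treatment can be tabulated as started before it

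*SAP*

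**What the plan says.** SAP 6.6.3 (Safety data) says that partial medication dates "will be imputed to enable subsequent calculation (but not for display", and calls the approach a worst case. For start dates there are two rules: "If the day of the start date is missing the start date is set to first day of the month", and "If the day and month of the start date are missing then the start date is set to 1st January of the year". Neither mentions first dose. Imputed end dates, in the same list, are bounded by a trial milestone; with the day missing, the month-end applies "or to the patient's trial completion date, if it is earlier than the last day of the month". Case-by-case review is reserved for what the rules leave open: "All other cases need to be assessed by the trial team on an individual basis, using the above points as guidance".

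SAP 7.2 then sorts medication by start date. One table holds "concomitant medication started and taken within the double-blind period", running from the day of first administration to the day before the Week 16 visit. Another holds medication whose start precedes first administration. A further table shows AD medication "used during the double-blind period (i.e., starting at baseline visit or thereafter". Restricted medication is also captured as an important protocol deviation, for example code D2.01c in SAP Table 6.2: 1: "Use of restricted medication (skin-related steroid) with potential influence on efficacy data".

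**The concern.** Setting a start as early as possible gives the longest exposure. SAP 7.2, however, uses the start date to decide whether a medication began before or during blinded treatment. For that decision, the earliest date favours the pre-treatment category, so the rule is not a worst case for showing escape use.

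The point has some weight because protocol 4.2.1 lets the investigator give standard of care of his or her choice if the disease worsens, possibly with trial treatment continuing. In the visible SAP, such use changes neither the primary model (7.4.1) nor the responder imputation (6.6.2), which is triggered by stopping study drug. The restricted-medication deviations exclude nobody from an analysis set. Apart from the deviation summary, the SAP 7.2 tables are therefore where a reader sees escape use by arm. Planned group sizes are 15 placebo and 30 active, so one misplaced patient shifts a percentage in these tables by 1/15 = 6.7 or 1/30 = 3.3 points.

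**Working it through.** The documents give no figure for the effect of this rule, so there is nothing to reproduce. The check applies the rule to every combination of Day 1 and true start date.

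**Inputs from the documents**
- Start-date rules: SAP 6.6.3.
- Day 1 is the day of first treatment and Week 16 is planned for Day 113 (SAP Table 6.7: 1). The double-blind medication table stops the day before the Week 16 visit, so starts after Day 1 fall on Days 2–112, which is 111 days.

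**Assumptions, not in the documents**
- Day 1 is equally likely on each date of a calendar year (2019 and 2020 tried).
- The true start is equally likely on each of the 111 days.

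**Day missing.** A record moves before Day 1 only if its true start is in the same calendar month as Day 1 and Day 1 is not the 1st. With Day 1 on date d (d ≥ 2) of a month of L days, L − d start days qualify. Summing over d = 2 to L gives (L − 1)(L − 2)/2, which is 435 for L = 31, 406 for L = 30, 378 for L = 29 and 351 for L = 28.
- 2019: (7 × 435 + 4 × 406 + 351) / (365 × 111) = 5,020 / 40,515 = 12.4%.
- 2020: (7 × 435 + 4 × 406 + 378) / (366 × 111) = 5,047 / 40,626 = 12.4%.
- Range by date of Day 1: 0% (for example on the 1st) to (31 − 2)/111 = 26.1% (on the 2nd of a 31-day month).

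**Day and month missing.** A record moves if its true start is in the same calendar year as Day 1 and Day 1 is not 1 January. With Day 1 on day j of the year (j ≥ 2), min(111, 365 − j) start days qualify in 2019.
- 2019: j = 2 to 254 gives 253 × 111 = 28,083; j = 255 to 365 gives 110 + 109 + … + 0 = 6,105. The total is 34,188 / 40,515 = 84.4%.
- 2020: (254 × 111 + 6,105) / 40,626 = 34,299 / 40,626 = 84.4%.
- Range: 0% (Day 1 on 1 January) to 100% (Day 1 early enough that all 111 days fall in the same year).

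**Examples**

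| Day 1 | True start | Day missing | Day and month missing |
|---|---|---|---|
| 10 Sep 2019 | 24 Sep 2019 | 1 Sep 2019: moved | 1 Jan 2019: moved |
| 10 Sep 2019 | 24 Oct 2019 | 1 Oct 2019: stays | 1 Jan 2019: moved |
| 20 Nov 2019 | 20 Jan 2020 | 1 Jan 2020: stays | 1 Jan 2020: stays |

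**Where a moved record goes**
- It leaves the table of medication started in the double-blind period.
- It enters the table of medication started before that period. It does not become historical medication: that needs a stop date before first infusion as well, and a partial stop date is imputed late, not early. SAP 7.2 still counts it as concomitant, because it appears to be ongoing at first dose.
- It leaves the AD-medication table, which requires a start at the baseline visit or later and has no route for medication ongoing at first dose.

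**The case against.** The case on the other side is substantial.

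- *Partial dates may be rare where it matters.* Escape treatment is chosen by the investigator, concomitant therapy is reviewed at each visit (protocol Flow Chart), unscheduled visits are documented with their reason (protocol 6.2.2.2), and the start date is a source-data item (protocol 8.3.1). An escape steroid begun under observation and recorded with only a year is hard to picture. This stands: the 84% may apply to almost no records, and no effect on this trial is shown.
- *Earliest start with latest end is a coherent worst case for exposure,* and the rule sits under safety data. This also stands, but SAP 7.2 uses the same dates for a different question. Elsewhere the SAP resolves a comparable doubt towards treatment: under 7.8.1 an adverse event on the day of first administration without a start time is assigned to the on-treatment phase.

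Three stronger readings are tempting, and the documents do not support them.

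- *That the rule generally moves in-trial steroids to before baseline and loses them.* Complete dates are untouched. Under the assumptions above about 88% of month-only dates stay on treatment, and the moved records remain in another table and in the listings.
- *That a moved record would be taken for a wash-out failure instead of in-trial restricted use.* In SAP Table 6.2: 1, D1.01 is checked against the medication end date, D2.01a–c by manual review of the listing, and A2.03 and A2.04 partly by manual review. Imputed dates are not displayed, so reviewers see the partial date as recorded.
- *That the EASI comparison is affected.* No visible text uses these dates in the primary model, the responder imputation or the analysis-set definitions. Parts of the SAP are blacked out, so use elsewhere can be neither shown nor excluded.

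**Conclusion.** The point holds as a minor defect in the descriptive medication tables. It concerns only partial start dates whose recorded month, or year if only that is known, contains Day 1. For those, a medication truly started on blinded treatment is tabulated as started before it and drops out of the AD-medication table. The expected share is about 12% of month-only dates and about 84% of year-only dates, given uniform Day 1 and uniform starts over Days 2–112. Escape treatment concentrated early after Day 1 would raise the month-only share, and later use would lower it. The number of affected patients cannot be computed, because the documents do not give the number of partial dates. This is a worthwhile improvement, not a threat to the trial's conclusions.

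**What to change.** Add one sentence to SAP 6.6.3: if the recorded month (or the recorded year, when only the year is known) contains the date of first dose, and neither the stop date nor other recorded data shows use before first dose (for example, the medication was already recorded at screening), the start date is imputed as the date of first dose; otherwise the present rule applies. Later months and years need no change, because their first day already lies after first dose.

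For records without evidence of earlier use, the share of true on-treatment starts moved before Day 1 then falls from about 12% and 84% to 0%. The work is one SAP sentence and a small change to the date-imputation program.

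The cost is misplacement in the other direction. Some true pre-baseline starts in Day 1's month or year will count as on-treatment, and a year-only record whose true start was after Week 16 would also be placed at first dose. For judging escape use during blinded treatment, that is the cautious direction.

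The sentence does not resolve the similar boundary at Week 16. Under the present rule and the same uniform assumptions, about 17.5% of month-only and 88% of year-only true starts on Days 113–196 are given a date before the Week 16 visit. A footnote counting records with imputed start dates in each table would let the reader see whether any of this matters.
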